Specific Aim 1 (Primary Aim): Determine the efficacy of standard 8-week CBT-I intervention in recovering alcohol dependent subjects. Hypothesis 1: Alcohol dependent participants who receive CBT-I, compared to the QDT, will exhibit greater improvement on the ISI and more durable treatment gains on follow-up at 3 and 6 months. Secondary analyses will assess for group differences in sleep continuity (e.g., average SL, WASO, and TST) over all time points and will evaluate these parameters relative to the meta-analytic norms.

Specific Aim 2: Investigate whether the alcohol dependent Veterans treated with CBT-I have reduced recidivism compared to those in the QDT control condition. Hypothesis 2: Alcohol dependent participants who receive CBT-I, compared to QDT, will exhibit a significantly higher percentage of days abstinent. Secondary analyses will assess for group differences on other alcoholism-related outcomes (e.g., craving, drinks per drinking day, and proportion of heavy drinking days).

Specific Aim 3: Evaluate if subjects treated with CBT-I have a greater improvement in daytime functioning as compared to subjects in the QDT. Hypothesis 3: Alcohol-dependent participants treated with CBT-I will exhibit greater improvement in subjective daily functioning (health-related quality of life [primary end point]), as well as anxiety and depressive symptoms [secondary end points]).

Exploratory Aim(s): Assess the potential relevance of genetic and neurobiologic factors as predictors of illness severity and treatment outcome. Specifically, family history of alcoholism and actigraphic data will be acquired during the course of the proposed project and evaluated for their relevance as correlates of clinical course.

J. **Primary Outcome Variable(s):**

- a) The primary sleep outcome measure for the study is the insomnia severity (as assessed with the Insomnia Severity Index scale (ISI)^{19,20};
- b) The primary alcohol outcome measure is percentage days abstinent (as assessed using the Timeline Follow Back measure (TLFB)²¹⁻²⁶).

K. **Secondary Outcome Variable(s):**

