- a) The secondary sleep outcome measures are the traditional five sleep continuity values that are obtained from the daily sleep diaries (averaged as weekly values for sleep latency [SL], number of awakenings [NWAK], wake after sleep onset [WASO], total sleep time [TST] and SE%); other outcome measures will include Pittsburgh Sleep Quality Index (PSQI), Composite Scale of Morningness (CSM), Knowledge Assessment Questionnaire (KAQ), the Treatment Evaluation Questionnaire (TEQ), and pre- and post-treatment evaluation questionnaire, Columbia-Suicide Severity Rating Scale Baseline version (CSSR-B) & Columbia-Suicide Severity Rating Scale Follow-up Screener (CSSR-S-FS), and the Epworth Sleepiness Scale (ESS). In a subset of subjects the polysomnographic sleep variables (sleep onset latency, sleep efficiency, wake after sleep onset time) will also be evaluated.
- b) The secondary alcohol measures are alcohol craving (assessed with Penn Alcohol Craving Scale, PACS)²⁷⁻³⁰, number of drinks per drinking day, and percent of heavy drinking days (assessed with the TLFB)²²⁻²⁶, Short Index of Problems (SIP).
- c) The outcome measures for health and mood are the Short Form-12 item scale (SF-12)³¹, the Patient Health Questionnaire 9-item scale (PHQ9)^{32,33}, the Generalized Anxiety Disorders 7-item scale (GAD7)^{34,35}, the Beck Depression Inventory-II scale (BDI-II)^{36,37} and the State-Trait Anxiety Inventory (STAI)³⁸, Columbia Suicide Severity Rating Scale (C-SSRS-B), and the Barratt's Impulsivity Scale (BIS), Interpersonal Support Evaluation List (ISEL), and Addictions Severity Index (ASI), Columbia-Suicide Severity Rating Scale Baseline version (CSSR-B) & Columbia-Suicide Severity Rating Scale Follow-up Screener (CSSR-S-FS).
- d) Family History of Alcohol Dependence will be assessed using the Semi Structured Assessment of the Genetics of Alcoholism (SSAGA) – Family History Assessment Module (FHAM)^{39,40}.
- e) Other drug use will be assessed using the SCID-I module for abuse and dependence on other drugs⁴¹ as well as with a Urine Drug Screen (UDS). See Figure 1 and Table 1 for details.

L. Study Design and Methods:

1. Is this a clinical trial? YES NO
- 1.1. If yes, what type? Check all that apply. N/A
 Phase I Phase II Phase III Phase IV
- 1.2. If yes, this study must be registered on Clinicaltrials.gov.

2. Design

- 2.1. What research methods will be used in the project? Check all that apply.

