- Emergence of another substance abuse problem which necessitates inpatient admission or a more aggressive treatment than provided by the protocol.
- Subject is incarcerated for more than a week.

Study participation can be restarted after consultation with the research physician for subjects who 1) return to treatment after a period of brief absence of less than 3 weeks, or 2) return to treatment after brief inpatient hospitalization of less than 2 weeks or additional outpatient treatment. Restarting study procedures is contingent upon clinical need and continuing to meet inclusion and exclusion criteria.

3. **Explain if survival data is required. If so, clarify how data will be obtained.** We will not be assessing for survival data in this pilot study. However we may consider looking at the survival data if there are a significant number of drop out of subjects from the study, with the end point of the survival analysis being the drop out date (i.e. total duration of participation in the study).
4. Not Applicable; subjects not recruited; chart review.

T. Risk/Benefit Assessment

1. Potential Study Risks

- 1.1. Describe and assess all of the following risks that may be associated with the research:
 - 1.1.1. Physical
 - a. Portable Sleep Apnea Monitoring: there may be discomfort associated with the use of nasal cannulas and sensors on the chest/abdomen;
 - b. Overnight Polysomnography: Sleeping in the CMCVAMC sleep laboratory with adhesive leads on the body may be associated with physical discomfort;
 - 1.1.2. Psychological
 - a. Sleep Restriction: patients may experience an increase in the daytime sequelae of insomnia as a result of this intervention (the scheduling of time in bed so as to equal average total sleep time). In the first few days of treatment this is likely to entail some sleep deprivation (~1 hour less sleep than is normal for the individual) and result in a transient increase in daytime sleepiness, fatigue, concentration problems, and irritability;
 - b. Data Collection during the Study: there may be discomfort associated with talking about family history of alcoholism, psychiatric issues and addiction-related issues. Furthermore, in some cases, the use of the sleep diaries and actigraphs may lead to (or be perceived as causing) a transient worsening of insomnia symptoms at home;

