 - c. Relapse to Alcohol: there is a possibility that the transient "side effects" of CBT-I may lead some individuals to resort to occasional alcohol use and that such behavior may also lead to relapse (heavy drinking);
 - d. Use of Other Drugs: there is a possibility that the transient "side effects" of CBT-I may lead some individuals to start using other drugs while taking part in the study-related procedures;
 - e. Suicidal/Homicidal Ideation. While there is no evidence that CBT-I increases suicidal or homicidal ideation, it is a possible consequence of the transient sleep deprivation that occurs with CBT-I. That is, sleep deprivation may lead to decreased inhibition in the frontal brain areas, which may, in turn, lead to a failure to inhibit or cope with such thoughts, especially in vulnerable populations like those who suffer from alcoholism.
 - 1.1.3. Social. A decreased interest in affiliating with other people because of persisting insomnia or a transient increase in the insomnia secondary to the sleep restriction associated with the CBT-I.
 - 1.1.4. Economic. Time spent participating in the study may interfere with the subject's ability to seek employment or participate at his job.

- 1.1.5. Monetary. May be secondary to loss of time spent in participating in the study.
 - 1.1.6. Legal. An increase in the drowsiness may lead to potential risk of a motor vehicle accident.
 - 1.1.7. Loss of confidentiality a. there is a possibility that the subject's identifying data and/or study information may be viewed by non-study personnel.
 - 1.1.8. Assess the likelihood and seriousness of such risks. Although the risks associated with drowsy driving are serious, the likelihood of this risk is low. The likelihood of the other risks are variable, between a low to a moderate level, and specific to the Veteran's individual situation.
 - 1.1.9. Other. N/A
- 1.2. Specify what steps will be taken to minimize these risks.
- a. Portable Sleep Apnea Monitoring: While the use of nasal cannulas and sensors on the stomach and abdomen are required for this screening, subjects that experience discomfort during orientation will be provided (where possible) the opportunity to select from different types of cannulas and sensors .

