 - e. Confidentiality: During the participation in this study, the patient will be assigned a 4-digit unique identification number. This number will not be derived from PHI of any sort (e.g., DOB, SSN, etc.) and will simply represent the study and the subject's recruitment number (e.g., 1001). Study numbers will be linked to subject identifiers in one spreadsheet that will be stored on the PI's password-protected VA online drive. These efforts make it very unlikely that the subject's identifying data and/or study

information may be viewed by non-study personnel. The data will now be captured and stored within the VA Redcap and stored in the secured VA servers.

- f. Relapse to the Drinking. All drinking behavior will be monitored. Monitoring will be based upon self-report items on the daily sleep diaries and clinical interviews by the principal investigator during the outpatient visits. These variables will be monitored for both research and clinical purposes. The research purpose is to determine how alcohol use varies with treatment for insomnia. The clinical purpose is to be able to determine if there has been a resumption of heavy drinking (four standard alcoholic drinks on any day or ≥ 14 drinks a week). If there is a resumption of sustained heavy drinking and this sustained heavy drinking places the subject at risk of medical, psychological or physical harm, then he will be withdrawn from the study, and a referral to the ARU or the inpatient unit, as deemed necessary for further treatment, will be offered to the participant
- g. Use of Other Street Drugs. Patients will be evaluated for the use of other street drugs through structured assessment instruments. Further, if there is a history of regular drug use, the subject will be regularly monitored with standard urine tests (note: this will be a condition for admittance into the study). If regular drug use is detected, the subject will be withdrawn from the study, and a referral to the ARU for further treatment will be offered to the participant.

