model. In this model, the mean ISI depends on fixed covariates and random effects⁵⁷. The fixed covariates of interest include time, treatment assignment, the interaction between time and treatment assignment, adjusting for family history of alcoholism and confounding variables identified in the preliminary analysis. The random effects represent the unobserved factors that lead to variation of the individual participant's outcome. Random intercepts for each participant permit modeling of natural variation across participants at baseline in the outcome of interest. In addition, random slopes or random effects for the trajectory of each participant over time allow for variation of each participant about a mean, overall trajectory across all participants. Estimates of the random effect for an individual participant also permit far more focused investigations of those individuals who depart from the mean over time and experience either better or worse than average change in outcome. Thus, the mixed effects longitudinal model permits both comparisons of groups as well as contrasts of individuals. Although less robust to model misspecification, the mixed effects paradigm offers special flexibility in longitudinal data when exposures vary over time and when dropout and missed visits lead to unbalanced groups. ISI and quality of life are continuous measures and most likely follow a symmetric or approximately normal distribution. Therefore the linear mixed regression model is appropriate. If departures from normality are found, we will consider transformations or other distributional forms that may better fit the data. The alcoholism-related outcome measures are counts (e.g. number of days abstinent, number of heavy drinking days, etc.) but will be summarized as percentages (e.g. percent abstinent days) and will also most likely follow a normal distribution. The target of inference is the participant-specific response to treatment over time. Specifically we are interested in the efficacy at the end of treatment (8 weeks) and durability after 3 and 6 months of follow-up. At each time point of interest, we will estimate from the fitted model the difference from baseline in the outcome for each treatment group and test the difference between these differences. The treatment effects will be the contrasts that represent the difference of differences from baseline in outcome across treatment groups at 3 and 6 months. Both univariate and multivariate results will be reported in terms of Wald test, point estimates, and 95% confidence intervals.

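### The plan gives no between-arm estimate of drinking, sleepiness, suicidal ideation or adverse events in the treatment weeks, when the protocol places the risks of sleep restriction

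*Combined protocol and SAP*

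**What the plan says.** **Timing of the risk.** Section L.2.1 places sleep restriction in sessions 2 and 3 of eight. Section T.1.1.2(a) says of it: "In the first few days of treatment this is likely to entail some sleep deprivation", followed by a transient rise in daytime sleepiness. T.1.1.2(c) treats relapse as a possibility: the transient effects "may lead some individuals to resort to occasional alcohol use and that such behavior may also lead to relapse (heavy drinking"). T.1.1.2(e) says there is no evidence that CBT-I increases suicidal or homicidal ideation, but adds that "it is a possible consequence of the transient sleep deprivation that occurs with CBT-I".

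**Timing of the analysis.** V.4.2 applies one mixed model to insomnia severity, abstinence and quality of life (Aims 1-3). Its time points are set out as follows: "Specifically we are interested in the efficacy at the end of treatment (8 weeks) and durability after 3 and 6 months of follow-up". It then states: "The treatment effects will be the contrasts that represent the difference of differences from baseline in outcome across treatment groups at 3 and 6 months".

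**Other comparisons.** Aim 1 in section I adds: "Secondary analyses will assess for group differences in sleep continuity (e.g., average SL, WASO, and TST) over all time points". Aim 2 lists secondary comparisons of craving, drinks per drinking day and heavy drinking days without naming a time point. V.4.2 also plans trajectory plots by arm.

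**Data bearing on harm.** T.1.2(f) says of drinking: "Monitoring will be based upon self-report items on the daily sleep diaries and clinical interviews by the principal investigator during the outpatient visits", and gives this monitoring a research purpose as well as a clinical one. Section K lists the Epworth Sleepiness Scale (ESS) and the C-SSRS follow-up screener as outcomes. V.4.2 describes no analysis of either by name, and none of adverse events.

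**The concern.** The participants are in recovery from alcohol dependence, and section I's preamble argues that a positive result could support a better standard of care. Whether the opening weeks of CBT-I provoke drinking is therefore part of what a reader of the results will need to know. The protocol identifies when the risk would arise and collects daily drinking data through that period, but the stated treatment effects fall after it. A transient excess of drinking or sleepiness on CBT-I could resolve by week 8 and leave little trace in the estimates the plan commits to report.

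Retention adds a second difficulty. S.2 lists sustained heavy-drinking relapse during treatment among the grounds for discontinuation or withdrawal from the study, and T.1.2(f) provides for withdrawal when such drinking puts the participant at risk of harm. S.1 says participants discontinued from the intervention are still followed to 8 weeks and to 3 and 6 months. Read together, these passages leave it unclear whether a participant who relapses early contributes later data. If not, the late contrasts lose the participants most affected.

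**Working it through.** **1. The plan's own figure.** V.4.1 gives 43 per group, about 30 after 30% attrition, two-sided alpha 0.025, intra-class correlation 0.3 and up to 10 follow-up measures.

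- Variance factor for a mean of 10 measures: (1 + 9 × 0.3)/10 = 0.37; square root 0.608.
- Detectable effect at 80% power with 28 per group: (2.241 + 0.842) × √(2/28) × 0.608 = 0.50 SD. With 30 per group it is 0.48 SD.
- With the plan's SD of 15.96 for abstinent days: 0.50 × 15.96 = 7.98 points.

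The stated 0.50 SD and 7.98 points reproduce. They are efficacy figures; the documents give no precision or power figure for any harm.

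**2. What a late contrast would see.** The documents do not state the window for percent days abstinent at each visit. Assume a dip of D points lasting L days. Over a cumulative 56-day treatment window it appears as D × L/56. In a window that excludes the dip, a dip that has fully resolved appears as 0.

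| Assumed dip | Over 56 days | Stated detectable difference |
|---|---|---|
| 10 points, 21 days | 3.75 | 7.98 |
| 20 points, 14 days | 5.0 | 7.98 |
| 30 points, 14 days | 7.5 | 7.98 |
| 30 points, 21 days | 11.25 | 7.98 |

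Only the largest and longest of these dips exceeds the plan's threshold.

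**3. What a direct early estimate would give.** Assume the SD of 15.96, which V.4.1 labels a pre-post SD, also applies to a short window.

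- 43 per arm: SE = 15.96 × √(2/43) = 3.44; 95% half-width = 1.96 × 3.44 = 6.7 points.
- 30 per arm: SE = 15.96 × √(2/30) = 4.12; half-width = 8.1 points.

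Normal approximation, two-sided 0.05:

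| Assumed true dip | Contrast | Effect seen | Power, 43 per arm | Power, 30 per arm |
|---|---|---|---|---|
| 10 points, 21 days | weeks 2-4 | 10 | 83% | 68% |
| 10 points, 21 days | all 56 days | 3.75 | 19% | 15% |
| 10 points, 7 days | weeks 2-4 | 10 × 7/21 = 3.3 | 16% | 13% |
| 10 points, 5 days | weeks 2-4 | 10 × 5/21 = 2.4 | 11% | 9% |

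The 83% requires a dip that fills the chosen window exactly. T.1.1.2(a) speaks of the first few days of treatment, so the shorter rows are at least as relevant. This favours week-by-week estimates over one fixed three-week block.

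**4. Rare events.** With no positive screens among 43, the exact upper 95% bound is 1 − 0.05^(1/43) = 6.7% one-sided, or 1 − 0.025^(1/43) = 8.2% two-sided. For a binary harm at assumed rates of 5% on QDT and 15% on CBT-I, power is about 34% with 43 per arm and 25% with 30. Counts and intervals are therefore the useful form; significance tests would say little.

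**The case against.** The strongest reply is that the plan is not blind to the early weeks. Sleep continuity, including total sleep time, is to be compared over all time points, and this measures the sleep loss from which the other risks are said to follow. The secondary alcohol comparisons carry no time restriction, the model contains a treatment-by-time interaction over up to ten follow-up measures, and trajectories are plotted by arm. Drowsiness is monitored at visits, drinking by diary and interview, suicidal ideation has a referral pathway, and adverse events go to the IRB and the data monitoring committee (T.1.2, V.2). A relapse that persists would still show at week 8 or later.

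Much of this stands, and it rules out several stronger readings that a reader might infer:

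- That every planned comparison is late. The sleep-continuity analysis shows otherwise.
- That the protocol expects relapse and ideation. Only sleep loss is called likely; relapse is a possibility, and for ideation the protocol says there is no evidence of an increase.
- That early harm would be missed altogether or reported as absent. Clinical monitoring exists, and no passage infers safety from the efficacy contrasts.
- That the C-SSRS would be analysed as a change between its baseline and follow-up forms. The change-from-baseline model is specified for the Aims 1-3 outcomes, and no such C-SSRS analysis is stated.

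The reply does not supply the missing estimate. Sleep continuity does not measure drinking, daytime sleepiness or ideation. Plots give no interval. An interaction term with no early contrast named commits the trial to no early result. Monitoring and reporting protect individuals but do not compare the arms.

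**Conclusion.** The point holds as a gap in prespecification. V.4.2 contains no between-arm estimate of drinking, sleepiness, suicidal ideation or adverse events for the treatment weeks, although the protocol ties the risks of its active treatment to the early part of that period. Late contrasts would dilute a short worsening, or not show it if it had resolved. The extent depends on the size and length of the dip, on the window used for percent days abstinent and on the SD in a short window, none of which the documents give; the 10-point, 21-day example is an illustration only.

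The passages on withdrawal after relapse and on continued follow-up must be reconciled, because they determine who remains in the late contrasts. This is a change the plan should make. It does not undermine the efficacy analysis.

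**What to change.** Add to V.4.2 a descriptive safety summary by arm, in all randomised participants and explicitly outside the efficacy alpha:

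1. Percent days abstinent, and the proportions with any drinking and any heavy-drinking day, from the daily diaries (and the TLFB where scheduled), by treatment week and over weeks 1-8, as CBT-I minus QDT differences with 95% confidence intervals.
2. ESS change from baseline, and counts of participants with a positive post-randomisation C-SSRS follow-up screen, at the visits where Table 1 schedules these instruments.
3. Counts of participants with adverse events, with serious adverse events, and with discontinuation by reason, with exact 95% confidence intervals.

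State that a neutral or favourable result at week 8, 3 months or 6 months will not be read as evidence of no early harm. Reconcile S.1, S.2 and T.1.2(f) on whether participants who relapse are followed. S.2 and T.1.2(f) also give different thresholds for heavy drinking; reconcile these so that item 1 rests on one definition.

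The cost is analysis text and a few tables, with no effect on the efficacy tests. The drinking part uses data already planned in the daily diaries. The visit marks in Table 1 are not legible in the text available, so the weeks covered by ESS, C-SSRS and TLFB need checking against the original. The drawback is imprecision: about ±7 points for abstinence with 43 per arm (±8 with 30), if the plan's SD applies, and wide intervals for rare events.

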- 4.2. **Define plans for data and statistical analysis, including key elements of the statistical plan, stopping rules and endpoints.** *Overview:* Our study proposes a longitudinal repeated-measures parallel-group design. This powerful design, with a baseline measurement and up to ten follow-up measures per participant over 6 months, allows for comparisons within each participant over time as well as across participants (treatment groups). The main analysis will look at differences between intervention groups in the changes in outcomes over time (i.e. insomnia severity, alcoholism-related outcomes and daily functioning). *Randomization:* Patients will be recruited and randomized as individuals. Allocation will be uniform across the two groups after suitable blocking and stratification on family history of alcoholism to ensure optimal balance of participant characteristics and to observe relationships between groups with and without a family history of alcoholism in the Exploratory Aim. Participants are randomly assigned to the CBT-I group, or the QDT group. The study biostatistician will create randomization sequences by family history of alcoholism (separate sequences) using a pseudo-random number generator with block sizes of 4. Two boxes of sequentially numbered, sealed, opaque envelopes will be prepared using the randomization sequences and labeled "Family History" and "No Family History". At the time of randomization, the first envelope, in sequential order, is pulled from the appropriate box and opened to reveal the group assignment. All the staff conducting assessments will be blinded to the allocation of treatment arm with the exception of [name], the BSM treatment provider, [name] the person overseeing treatment allocation, and [name], the monitor for BSM treatment for the study. *Preliminary Analyses:* All data, regardless of the format, will first be assessed by [name] and his mentors for missing data, distributions of all observed measures, and out-of-range values by means of conventional descriptive tables. SAS v9.3 will be our primary tool for these analyses as the software is both mature and well-documented⁵⁶. Next, we will employ raw and smoothed plots to visualize the individual and average trajectories of all repeated measures over time according to assigned treatment and by participant characteristics. All questions of data quality and integrity will be investigated before any statistical modeling, since complete and accurate data are essential for unbiased estimates and confidence intervals. We will compare all baseline variables across groups to check the adequacy of randomization. The baseline comparisons will be based on: 1) t-test or Wilcoxon rank sum tests for continuous variables depending on the symmetry of the distributions; 2) on logistic regression for binary or ordinal variables; and 3) on Poisson log-linear regression for count data. If imbalances are found at baseline, then the relevant variables will be treated as confounders in the analysis.

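### The Aim 1-3 model leaves the arms' baseline means free and fixes no adjustment for the outcome's baseline value, giving up precision at 6 months that a constrained model would keep

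*Combined protocol and SAP*

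**What the plan says.** All of this is in section V, item 4.2 (Statistical Analysis).

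- **Baseline is a response.** The Overview describes "a baseline measurement and up to ten follow-up measures per participant over 6 months". The Aims 1-3 text adds: "Random intercepts for each participant permit modeling of natural variation across participants at baseline in the outcome of interest".
- **Baseline means are free.** "The fixed covariates of interest include time, treatment assignment, the interaction between time and treatment assignment". With a treatment main effect as well as the interaction, each arm has its own baseline mean.
- **Covariates.** The model is fitted "adjusting for family history of alcoholism and confounding variables identified in the preliminary analysis". Family history is the only covariate fixed in advance.
- **How confounders are chosen.** Under Preliminary Analyses: "We will compare all baseline variables across groups to check the adequacy of randomization". Variables found imbalanced then become confounders in the model. No threshold is given.
- **Random effects.** Random intercepts, plus "random slopes or random effects for the trajectory of each participant over time". The variances and the coding of time are not stated.
- **What is tested.** From the fitted model the plan will estimate "the difference from baseline in the outcome for each treatment group and test the difference between these differences". The treatment effects are the contrasts for "the difference of differences from baseline in outcome across treatment groups at 3 and 6 months"; efficacy at week 8 is also of interest.

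No section constrains the baseline means to be equal or names the outcome's baseline value as an unconditional covariate.

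**The concern.** Randomisation makes the true baseline means equal, so a fitted baseline difference between arms is noise. A difference of changes subtracts that noise in full. A model that knows the means are equal subtracts only the part that predicts follow-up.

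This matters in a small trial: section V, item 4.1 expects 30 per group after attrition. The baseline values are collected anyway.

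The imbalance rule does not fill the gap. It seldom brings in the useful covariate, and it lets the primary model's covariates depend on chance features of the data.

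**Working it through.** **The plan's own figure.** Item 4.1 states 80% power for 0.50 SD at 6 months, with ICC 0.3, two-sided level 0.025 and 30 per group after 30% attrition. Comparing arms on the mean of m = 10 equicorrelated follow-ups gives

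n = 2 × [1 + (m − 1) × ICC]/m × [(z₁ + z₂)/0.5]² = 2 × 0.37 × [(2.241 + 0.842)/0.5]² = 28.1, so 29 per group.

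This is close to the stated 30, and 30/0.7 = 42.9 gives the stated 43. The formula subtracts no baseline, so the plan's power figure does not measure the point at issue.

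**Two-visit case.** Let ρ be the baseline-to-follow-up correlation, k the baseline SD divided by the follow-up SD, and the follow-up variance 1. Per-patient variances are:

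- difference of changes: 1 + k² − 2ρk
- baseline means constrained equal (or baseline as covariate): 1 − ρ²

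Precision lost = 1 − (1 − ρ²)/(1 + k² − 2ρk) = (k − ρ)²/(1 + k² − 2ρk). With k = 1 this is (1 − ρ)/2: 45%, 35% and 25% at ρ = 0.1, 0.3 and 0.5. With k = 0.6 and ρ = 0.5 it is 0.01/0.76 = 1.3%. It is zero when k = ρ.

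**Full model.** I computed the generalised least squares variance of the 6-month contrast, first with free and then with equal baseline means.

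- From item 4.1: 43 per arm, 30% dropout by 6 months, ICC 0.1-0.5, ten follow-ups (the plan's upper limit).
- Assumed: dropout even across visits; ICC used as ρ; weekly visits to week 8, then 3 and 6 months later; s = slope variance at 6 months relative to intercept-plus-residual variance. Equal SDs means k = 1 before slope variance is added.

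Loss = 1 − Var(constrained)/Var(free). For categorical time, ICC 0.1, k = 1, s = 0: 1 − 0.0652/0.1029 = 36.6%, and √(0.1029/0.0652) = 1.256, so the planned SE is 25.6% larger.

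| Time coding | k | s | Loss at ICC 0.1 / 0.3 / 0.5 |
|---|---|---|---|
| Categorical | 1 | 0 | 36.6 / 28.1 / 20.0% |
| Categorical | 1 | 0.5 | 27.9 / 20.2 / 12.9% |
| Categorical | 0.8 | 0 | 25.9 / 16.6 / 8.2% |
| Categorical | 0.6 | 0 | 15.1 / 6.7 / 1.0% |
| Categorical | 1.2 | 0 | 46.3 / 39.3 / 32.8% |
| Linear | 1 | 0 | 22.5 / 10.1 / 5.0% |
| Linear | 1 | 0.5 | 16.0 / 6.7 / 3.0% |
| Linear | 0.8 | 0.5 | 14.0 / 4.9 / 1.5% |

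A ratio below 1 is plausible for the ISI, because entry requires at least 15 (section Q, item 2.1.1). A ratio above 1 is possible for abstinent days, because the baseline window covers the last 90 drinking days (section Q, item 2.3). Timing the follow-ups from baseline raises the linear losses at k = 1, s = 0 to 28 / 13 / 7%. With only three follow-ups and equal SDs the loss is 13-37% (categorical) or 13-48% (linear).

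**Imbalance rule.** At an assumed threshold of p < 0.05 or p < 0.10, the outcome's baseline is flagged in 5% or 10% of randomised trials, so the adjustment is absent in 90-95%. For 10 or 20 independent baseline variables at p < 0.05, at least one is flagged in 1 − 0.95¹⁰ = 40% or 1 − 0.95²⁰ = 64% of trials. Correlated scales lower this: an assumed common correlation of 0.5 gives about 29% and 42%.

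**The case against.** The strongest reply is that the planned analysis is legitimate and well matched to its hypothesis. Hypothesis 1 speaks of greater improvement, and a difference of changes tests that directly, without bias. That stands, and it makes this an efficiency point only.

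The second reply is that the size is not established. It depends on time coding, slope variance, SD ratio, number of follow-ups and reading the ICC as a correlation, and the documents settle none of these. That also stands. A reader might infer that the trial gives up over a third of its precision. With ten follow-ups and equal SDs, that needs categorical time and an ICC near 0.1, and it is a variance figure.

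The third concerns remedies that go too far.

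- Switching to categorical visits looks like a natural part of the fix. It guards against a misspecified trajectory, but with ten follow-ups the constrained categorical analysis has 1.01 to 1.37 times the variance of the planned contrast if time was to be linear. The plan leaves linear time open, so this is a separate trade-off.
- Modelling follow-up visits with baseline as a covariate drops participants who have no post-baseline value unless they are imputed. Item 4.2 promises to include everyone randomised and makes imputation conditional.

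Neither objection touches the constraint itself. With a separate baseline variance, it lowered the 6-month variance in every scenario run.

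**Conclusion.** The concern holds as an avoidable loss of efficiency. Under the stated assumptions with equal SDs, the precision given up at 6 months is about 13-37% with categorical time (SE 7-26% larger) and about 3-23% with linear time. It falls to near zero when the baseline SD is about 0.6 of the follow-up SD and the correlation is 0.5. The documents do not say where in this range the trial lies.

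Two stronger readings are not supported. A reader might infer that the test is biased or its error rate inflated; under randomisation the planned contrast is valid. A reader might also infer that the change would deliver the stated 80% power. At 0.5 SD, level 0.025, ICC 0.3, equal SDs, no random slopes and 30% dropout, power for the 6-month contrast rises from about 31% to 43% (categorical) or from 50% to 55% (linear), so a gap remains either way.

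Fixing the covariates in advance is worthwhile even where the precision gain is small.

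**What to change.** In the Aim 1-3 models, under whatever time coding the plan adopts:

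1. Constrain the arms' baseline means to be equal: no treatment main effect at baseline, treatment-by-time terms only.
2. Allow the baseline variance to differ from the follow-up variance.
3. Keep family history as the prespecified covariate and replace the imbalance-triggered confounder rule with this fixed set. The baseline tables can stay as description.
4. Keep the difference-of-changes contrast as a sensitivity analysis.

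Prefer this to the baseline-as-covariate form, so that all randomised participants stay in. State the time coding, but decide between linear and categorical visits on its own merits.

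The cost is a few lines of SAP wording and no new data. The effect becomes a baseline-adjusted difference, which needs a sentence linking it to Hypothesis 1; under randomisation the estimand is unchanged. Step 2 matters: with categorical time, if one common variance were fitted while the true SD ratio was 0.6 and the correlation 0.5, the constrained model would be about 3% less precise than the planned contrast.
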